9	STATISTICAL CONSIDERATIONS.....	38
9.1	Sample Size DeterminationError! Bookmark not defined.	36
9.2	Populations for Analyses	38
9.3	Analyses	36
10	STUDY MANAGEMENT	39
10.1	Compliance with the Protocol.....	39
10.2	Records Retention	40
10.2.1	Records Retention	40
10.2.2	Study Drug Records.....	40
10.3	Destruction of Investigational Product.....	41
11	GLOSSARY OF TERMS.....	42
12	LIST OF ABBREVIATIONS	43
13	REFERENCES.....	44

PROTOCOL SYNOPSIS

Protocol Title:	Apixaban versus warfarin for the management of post-operative atrial fibrillation: a prospective, controlled, randomized pilot study
Site Numbers & Names:	Sanford Medical Center, Fargo, ND
Research Hypothesis:	We hypothesize that there will be no significant differences between apixaban and warfarin anticoagulation strategies for the outcomes of venous thromboembolism/stroke or bleeding events when utilized for new-onset postoperative atrial fibrillation after isolated coronary artery bypass grafting (CABG).
Study Schema: Drugs / Doses / Length of Treatment)	
Patients who develop persistent atrial fibrillation after isolated coronary artery bypass grafting will be identified and randomized to anticoagulation with either warfarin (standard of care) or apixaban.
 
Warfarin will be dosed daily, with International Normalized Ratio (INR) monitoring per hospital protocol. After discharge, warfarin dosing will be managed by the anticoagulation clinic per protocol with a target INR of 2-3.
 
Apixaban will be dosed at 5 mg twice daily, or 2.5 mg twice daily in patients with at least two of the following characteristics: age \geq 80 years, weight \leq 60 kg, or serum creatinine \geq 1.5 mg/dL.
 
Patients will remain on anticoagulation until no longer needed (typically within 30 days of surgery). Study follow-up will be through the patient's 30-day follow-up appointment.

Study Objectives:	
1) Primary endpoint: freedom from stroke or thromboembolic event will be captured.
 
2) Secondary endpoints: -units of blood given after initiation of anticoagulation medication -total post-operative length of stay -duration from diagnosis of post-operative atrial fibrillation (POAF) to discharge from hospital -time in therapeutic range of INR if on warfarin -patient compliance percentage to apixaban if on apixaban
 
3) Safety assessments: major and minor bleeding events, as defined by the International Society on Thrombosis and Haemostasis, will be captured. Clinical events and blood product utilization will be identified and captured.

Study Design:	
In this open-label, prospective, randomized pilot study, patients who develop atrial fibrillation after isolated coronary artery bypass grafting surgery will be identified. Patients with persistent atrial fibrillation (>12 hours) or recurrent sustained atrial fibrillation (≥ 2 episodes of atrial fibrillation lasting longer than 30 minutes) will be candidates for inclusion. Upon meeting study inclusion and exclusion criteria, and after informed consent, patients will be randomized to either the standard of care (warfarin per protocol) or apixaban arms of the trial. Routine postoperative care after CABG will occur in both groups. Upon discharge, anticoagulation in both groups will be managed by the anticoagulation clinic. Patients will be followed for 30 days after surgery.

Accrual Goal: (Total number of subjects)	56 patients
Accrual Rate: (Number of subjects expected per month)	We anticipate enrolling 2-3 patients per month based on current projections.
FPFV: LPFV: Follow Up: (mm/dd/yy)	FPFV: 9/1/16 LPFV: 12/31/18 Follow up: 30 days per patient Final Report: 3/31/19

Correlative Studies: (PK/PD, etc.)
	
Retrospective analysis conducted at our facility:
 
Anderson E, Johnke K, Leedahl D, Dyke, C. Novel oral anticoagulants vs warfarin for the management of postoperative atrial fibrillation: clinical outcomes and cost analysis. American Journal of Surgery. Volume 210, Issue 6, 1095-1103²

Inclusion Criteria:
	
Patients diagnosed with new-onset persistent or recurrent atrial fibrillation after isolated CABG surgery. Persistent atrial fibrillation is defined as an episode of >12 hours. Recurrent atrial fibrillation is defined as 2 or more episodes of atrial fibrillation lasting longer than 30 minutes.


Exclusion Criteria:
	
 1. Patients undergoing valve replacement or with an artificial heart valve, or with moderate or severe mitral stenosis 2. Stroke within the previous 7 days. 3. Patients currently experiencing active bleeding precluding initialization of anticoagulation therapy in the opinion of their managing physician, or with increased bleeding risk (as determined by the attending surgeon) believed to be a contraindication to anticoagulation at the time of randomization. 4. Atrial fibrillation due to a reversible cause other than recent surgery 5. Planned major surgery requiring stoppage of anticoagulation therapy during the trial period. 6. Patients taking warfarin, apixaban, rivaroxaban, dabigatran, edoxaban, or enoxaparin at home for any indication in the 15 days prior to surgery. Patients taking clopidogrel or ticagrelor within 5 days prior to surgery, patients taking prasugrel within 7 days prior to surgery, and patients taking ticlopidine within 10 days prior to surgery. 7. Patients receiving clopidogrel, ticagrelor, prasugrel, or ticlopidine during the study period. 8. Patients diagnosed with persistent atrial fibrillation chronically before undergoing surgery. 9. Patients with paroxysmal atrial fibrillation requiring oral anticoagulation prior to surgery. 10. Severe renal insufficiency (serum creatinine level of >2.5 mg/dL or CrCL<25 ml/min) for consecutive measurements. 11. Patients who are pregnant or of child-bearing age. 12. Patients <18 years of age. 13. Patients unable to give informed consent
-----------------------------------	--

Criteria for Evaluation: (Efficacy, safety, stopping rules, etc.)
	
Efficacy will be measured by the freedom from systemic thromboembolism or stroke during the study period. Events relating to thromboembolism or stroke will be adjudicated using pre-determined definitions by independent committee members that remain blinded to the patient's treatment arm.
 
Safety, including major and minor bleeding will be quantified and defined by the Society on Thrombosis and Haemostasis, as described in section 6.4.2, subsection (2). Clinical events that occur during the study period will be quantified and measured, including adverse events, serious adverse events, blood product utilization, length of stay, duration of atrial fibrillation, and time to adequate anticoagulation.


Data Analysis Plan
	
Efficacy and safety data will retrospectively assessed and analyzed after the patient has completed the 30-day course of therapy. Events relating to thromboembolism or stroke will be adjudicated using pre-defined endpoint definitions by independent committee members that remain blinded to treatment arm. Safety events, including major bleeding will be as defined by the International Society on Thrombosis and Haemostasis.³ In the hospital, bleeding will be assessed daily by monitoring hemoglobin and the need for transfusions, and defined by a drop in hemoglobin of > 2 gm/dL in the previous 24 hours, or transfusion of at least two units of blood products. After discharge, we will monitor for readmissions related to bleeding, indicated by the need of transfusion of at least two units of blood products.

Statistics:
	
Continuous variables will be expressed as mean ± standard deviation or median with interquartile range (IQR) as appropriate. Continuous variables will be compared using t-tests for parametric data or Wilcoxon analysis for nonparametric data. We will complete the analysis in an intent-to-treat manner. We will include analysis for confidence intervals and other appropriate statistical tests to assess binary outcomes. We realize that statistical comparison between groups will be of limited utility in this pilot study as this study is not powered for comparison of events between groups. Data will be analyzed using JMP software, version 12.0.0 (Cary, NC).

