4.2 Study Population

4.2.1 Inclusion Criteria

1) Signed Written Informed Consent

- Before any study procedures are performed, subjects will have the details of the study described to them, and they will be given a written informed consent document to read. Then, if subjects consent to participate in the study, they will indicate that consent by signing and dating the informed consent document in the presence of study personnel. This informed consent will be scanned into the patient's EMR, as well as retained for a period not less than three years after the completion of the study.

2) Target Population

- Patients diagnosed with new-onset persistent or recurrent atrial fibrillation after isolated CABG surgery. Persistent atrial fibrillation is defined as an episode of >12 hours. Recurrent atrial fibrillation is defined as two or more episodes of atrial fibrillation lasting longer than 30 minutes.

3) Age and Reproductive Status

- Males and Females, at least 18 years of age
- Women of childbearing potential (WOCBP) must have a negative serum or urine pregnancy test (minimum sensitivity 25 IU/L or equivalent units of HCG) within 24 hours prior to the start of study drug. Patients undergoing isolated CABG must have this tested and documented prior to the procedure, and this will be verified prior to randomization.
- Women must not be breastfeeding.
- WOCBP must agree to follow instructions for method(s) of contraception for the duration of treatment with study drug(s): 30 days of treatment plus 5 half-lives of study drug Apixaban (3 days) or warfarin (8 days) plus 30 days (duration of ovulatory cycle) for a total of 38 days post-treatment completion.
- Males who are sexually active with WOCBP must agree to follow instructions for method(s) of contraception for the duration of treatment with study drug(s): 30

days of treatment plus 5 half-lives of study drug Apixaban (3 days) or warfarin (8 days) plus 90 days (duration of sperm turnover) for a total of 98 days post-treatment completion.

- Azoospermic males and WOCBP who are continuously not heterosexually active are exempt from contraceptive requirements. However they must still undergo pregnancy testing as described in this section.

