4.2.2 Exclusion Criteria

Target Disease Exceptions

- Atrial fibrillation due to a reversible cause other than recent surgery
- Patients diagnosed with persistent or paroxysmal atrial fibrillation chronically before undergoing surgery

- Patients with mechanical heart valves

Medical History and Concurrent Diseases

- Patients currently experiencing active bleeding precluding initialization of anticoagulation therapy in the opinion of their managing physician, or with increased bleeding risk (as determined by the attending surgeon) believed to be a contraindication to anticoagulation at the time of randomization Planned major surgery requiring stoppage of anticoagulation therapy during trial period
- Stroke within the previous 7 days
- Moderate or severe mitral stenosis
- Conditions other than atrial fibrillation that required anticoagulation (prosthetic mechanical heart valve)

Concomitant Medications

-
- Patients taking warfarin, apixaban, rivaroxaban, dabigatran, edoxaban, or enoxaparin at home for any indication in the 15 days prior to surgery. Patients taking clopidogrel or ticagrelor within 5 days prior to surgery, patients taking prasugrel within 7 days prior to surgery, and patients taking ticlopidine within 10 days prior to surgery
- Patients receiving clopidogrel, ticagrelor, prasugrel, or ticlopidine during the study period

Physical and Laboratory Test Findings

- Severe renal insufficiency (serum creatinine level of >2.5 mg/dL or CrCL<25 ml/min) for consecutive measurements

Allergies and Adverse Drug Reactions

- Allergies to warfarin or apixaban, or components of warfarin or apixaban

Sex and Reproductive Status

- *See Section on WOCBP above (Section 4.2.1, item # 3.)*

Other Exclusion Criteria

- Prisoners or subjects who are involuntarily incarcerated.
- Subjects who are compulsorily detained for treatment of either a psychiatric or physical (eg, infectious disease) illness.
- Patients <18 years of age.
- Patients unable to give informed consent.

Eligibility criteria for this study have been carefully considered to ensure the safety of the study subjects and to ensure that the results of the study can be used. It is imperative that subjects fully meet all eligibility criteria.

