4.2.4 Discontinuation of Subjects from Treatment

Subjects MUST discontinue investigational product (and non-investigational product at the discretion of the investigator) for any of the following reasons:

- Withdrawal of informed consent (subject's decision to withdraw for any reason).
- Any clinical adverse event, laboratory abnormality, or intercurrent illness which, in the opinion of the investigator, indicates that continued participation in the study is not in the best interest of the subject.
- Pregnancy
 - Instruct WOCBP to contact the investigator or study staff immediately if they suspect they might be pregnant (eg, missed or late menstrual period) at any time during study participation. Institutional policy and local regulations should determine the frequency of on-study pregnancy tests for WOCBP enrolled in the study.
 - The investigator must immediately notify BMS if a study subject becomes pregnant.

- Loss of ability to freely provide consent through imprisonment or involuntary incarceration for treatment of either a psychiatric or physical (eg, infectious disease) illness.
- While patients may request withdrawal from the study at any time, they will be advised to check with their medical provider before discontinuing any anticoagulant medication, for their safety.
- Subjects can voluntarily withdraw from the study at any time, but the investigators will continue to follow the patient so that an intent-to-treat analysis can be performed. Failure to take study medication as prescribed, or failure to follow up as directed with the anticoagulation clinic, will be noted in our analysis to the best extent we are able.
- Any data collected before withdrawal will be used for study outcomes, although it will be noted that the participant did not complete the 30-day course of therapy. Attempts will be made to determine and note the reason for withdrawal.
- All subjects who discontinue should comply with protocol-specified follow-up procedures outlined in Section 6. The only exception to this requirement is when a subject withdraws consent for all study procedures or loses the ability to consent freely (ie, is imprisoned or involuntarily incarcerated for the treatment of either a psychiatric or physical illness). If a subject withdraws before completing the study, the reason for withdrawal must be documented appropriately.

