6 STUDY ASSESSMENTS AND PROCEDURES

6.1 Time and Events Schedule

If a subject chooses to be removed from the study, withdraws informed consent, or if therapy must be stopped in the interest of the patient's safety, data collected to that point of the study will be collected for intent-to-treat analysis. We will document the reason for a patient's early withdrawal from the study, or the discontinuation of treatment for a patient by the patient's physician or study coordinator.

After the 30-day post-operative physician examination, there will be no further patient assessments. Analysis of all outcomes will be done by EMR analysis, except for treatment compliance as noted above.

Time and Events Schedule for Protocol: CV185-505

Procedure	Prior to Surgery (day of surgery, or <30 days prior)	After Diagnosis of AFib	Upon Hospital Discharge	At Each Anticoagulation Clinic Visit (warfarin)	At 30-Day Post-Operative Examination	After 30-Day Post-Operative Examination
Eligibility Assessments						
Informed Consent		X				
Medical History		X				
Inclusion/Exclusion Criteria		X				
Clinical Drug Supplies						
Randomize		X				
Dispense Study Treatment			X			
Patient Medication Consultation			X			
Safety Assessments						
Pregnancy Test for WOCBP	X					
Renal Function Test	X	X				
Hepatic Function Test		X				
INR measurement	X	X		X		
Monitoring for Bleeding Events			X	X	X	
Monitoring for Thrombotic Events			X	X	X	
Efficacy Assessments						
Measure Apixaban Adherence					X	
EMR Analysis of All Other Outcomes						X
Outcomes Statistical Analysis						X

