6.3 Safety Assessments

1) Major bleeding, as defined by the International Society on Thrombosis and Haemostasis based on the following criterion:

- a. Fatal bleeding, and/or
- b. Symptomatic bleeding that occurs in a critical area or organ, such as intracranial, intraspinal, intraocular, retroperitoneal, pericardial, in a non-operated joint, or intramuscular with compartment syndrome, assessed in consultation with the surgeon, and/or
- c. Extrasurgical site bleeding causing a fall in hemoglobin level of 20 g/L (2g/dL) or more, or leading to transfusion of two or more units of whole blood or red cells within 24-48 hours of the bleeding and/or
- d. Surgical site bleeding that requires a second intervention – open, arthroscopic, endovascular- or a hemarthrosis of sufficient size as to interfere with rehabilitation by delaying mobilization or delayed wound healing, resulting in prolonged hospitalization or a deep wound infection, and/or
- e. Unexpected surgical site bleeding, prolonged and/or sufficiently large to cause hemodynamic instability, as assessed by the surgeon, with a fall in hemoglobin of at least 20 g/L (2g/dL) or transfusion of two or more units of whole blood or red cells within 24 hours of the bleeding.³

2) Clinical relevant non-major bleed, defined as any notable bleeding not classified as major.

3) Pregnancy tests will be performed pre-operatively on the day of surgery for all WOCBP, via urine hCG screening.

4) A baseline renal function panel will be obtained either pre-operatively or within 30 days of surgery. The renal function panel includes: glucose, BUN, creatinine, BUN/creatinine ratio, sodium, potassium, bicarbonate, chloride, calcium, phosphorus, albumin, and anion gap.

5) The hepatic function test panel will be ordered before initiating warfarin (if a recent baseline is not available). This panel includes: total protein, albumin, alk phos, AST, ALT, total bilirubin, direct bilirubin, and indirect bilirubin.

6) INR will be checked before surgery to ensure the patient's INR is within normal limits in preparation for their surgery, regardless of whether they were previously on warfarin, and again upon initiation of warfarin therapy. INR will be checked daily in the hospital, and at each visit to the anticoagulation clinic. These visits are usually scheduled within three days of discharge from the hospital, then twice weekly until the INR is therapeutic, then weekly for the duration of the study.

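### The synopsis excludes all patients of child-bearing age but section 4.2.1 admits them; if 4.2.1 governs, the only scheduled pregnancy test is too old for AF starting on post-operative day 2 or later

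*Combined protocol and SAP*

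**What the plan says.** The synopsis, in exclusion item 11, rules out "Patients who are pregnant or of child-bearing age", with no exception.

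The body takes a different line. Section 4.2.1, item 3, sets conditions on which WOCBP may enter: contraception during and after treatment, no breastfeeding, and a negative serum or urine test "within 24 hours prior to the start of study drug". The same bullet adds: "Patients undergoing isolated CABG must have this tested and documented prior to the procedure, and this will be verified prior to randomization". Under sex and reproductive status, the 4.2.2 exclusion list has only a pointer, "See Section on WOCBP above (Section 4.2.1, item # 3". Section 4.2.3 defines WOCBP. Section 4.2.4 provides for such women once they are in the trial: "Institutional policy and local regulations should determine the frequency of on-study pregnancy tests for WOCBP enrolled in the study".

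On timing, 6.3 item 3 states: "Pregnancy tests will be performed pre-operatively on the day of surgery for all WOCBP". The 6.1 schedule has one row for this, "Pregnancy Test for WOCBP", with a single mark before surgery and none after AF diagnosis. Consent, the eligibility check and randomization are all placed after AF diagnosis.

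**The concern.** There are two linked problems. First, the synopsis and the body give opposite answers on eligibility. This is not a case of a synopsis shortening the body text, because one excludes a group and the other admits it on conditions.

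Second, if the body rule is the operative one, the schedule does not provide the test that the rule calls for. The test is tied to surgery and the 24-hour limit to the first dose. Between the two lie the operation, the onset of AF, the time AF needs to qualify, consent and randomization.

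What is at stake is a safety criterion, not an estimate. The protocol requires study drug to be stopped in pregnancy and pregnancies to be handled as SAEs, with reporting within 24 hours. Dosing a WOCBP on an out-of-date test would breach a written inclusion criterion.

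**Working it through.** **Part 1: the two eligibility rules side by side**

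- A WOCBP who tests negative in time, is not breastfeeding and accepts contraception is excluded by synopsis item 11 and eligible under 4.2.1.
- A woman of child-bearing age who has had a hysterectomy is excluded by item 11. She is not a WOCBP under 4.2.3, so the body neither excludes her nor requires a test.

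The lists differ in outcome and also in concept: age in one, reproductive potential in the other. The body looks like the intended rule, since 4.2.1, 4.2.3 and 4.2.4 define these women, set their conditions of entry and cover them on study. The documents do not say which text prevails.

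**Part 2: age of the scheduled test at first dose, if the body governs**

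The 24-hour limit is a stated rule, so there is no derived figure to reproduce. Inputs:

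- Test: pre-operative, on day 0, the day of surgery (6.3 item 3; 4.2.1 also says before the procedure).
- AF onset: most common in the first four post-operative days, with the peak on day 2 (1.1).
- Minimum time from onset to qualifying: 12 h by the persistent route; 2 × 0.5 h = 1 h by the recurrent route (4.1, 4.2.1).
- First dose: in hospital, after AF qualifies (4.1) and after randomization.

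To favour the plan as far as possible, put the test at the last moment of day 0, AF onset at the first moment of day d, no gap between recurrent episodes, and no delay for consent or randomization. Then:

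minimum test age = (d − 1) × 24 h + qualifying time

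| AF onset | Recurrent route | Persistent route |
|---|---|---|
| Day 2 | 24 + 1 = 25 h | 24 + 12 = 36 h |
| Day 3 | 48 + 1 = 49 h | 48 + 12 = 60 h |
| Day 4 | 72 + 1 = 73 h | 72 + 12 = 84 h |

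Every entry exceeds 24 h. These are floors, not typical values, because a pre-operative test cannot really be done at midnight at the end of day 0. A test at 18:00, 12:00 or 06:00 on day 0 is already 48 − 18 = 30 h, 48 − 12 = 36 h or 48 − 6 = 42 h old when day 2 begins, before any qualifying time is added.

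**Whether another provision fills the gap**

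Checking the pre-procedure result before randomization confirms an existing result and does not renew it. The 4.2.4 sentence on test frequency concerns women already enrolled and is not tied to the first dose. No other test is scheduled. By contrast, 6.1 does repeat renal function and INR after AF diagnosis.

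**The case against.** **The second part depends on the first.** If item 11 prevails, no WOCBP is enrolled and the timing question disappears. Section 4.2.2 insists that all criteria be met, so a cautious site applying both lists would follow the stricter one. This stands: the timing gap is conditional on the body governing. The conflict between the lists remains in either case.

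**The pre-procedure test may be how CABG patients are meant to satisfy the rule.** That instruction directly follows the 24-hour clause, and the protocol carries other generic wording that does not fit this trial, such as a placebo lead-in (7.2.1) and a follow-up skin biopsy (7.1.1). The 24-hour clause may be similar leftover text. This is a fair reading of intent, and the documents do not prove that a second test was planned. But every participant is a CABG patient, so on this reading the limit would bind nobody. The bullet needs correcting either way.

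**A reader might infer more than the text supports:**

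- That a test up to 30 days old is allowed, from the 6.1 column heading "Prior to Surgery (day of surgery, or <30 days prior". That column is shared with the renal test, for which 6.3 item 4 gives the 30-day window. Item 3 fixes the pregnancy test to the day of surgery.
- That the scheduled test is always out of date. For AF on day 1 this turns on clock times that the documents do not give.
- That the criterion cannot be met, or that women will be dosed on expired tests. Eligibility is checked after AF diagnosis and nothing forbids an unscheduled hCG. The weakness is that this relies on staff noticing.

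**Conclusion.** The point holds as an internal inconsistency of low severity. The conflict between synopsis item 11 and section 4.2.1 is plain on the text. The timing failure follows if the body governs: for any AF starting on post-operative day 2 or later, the day-of-surgery test is more than 24 hours old at first dose, by at least 1 hour (25 − 24) on the recurrent route and 12 hours (36 − 24) on the persistent route. This needs no assumption about the hour of the test.

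The number of women affected cannot be computed. The documents give no share of WOCBP, and section 1.1 places the highest risk of post-operative AF at advanced age, so it may be zero among 56 patients. No endpoint, sample size or analysis is touched.

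**What to change.** Choose one rule and use it in both places. The documents do not settle which, so the sponsor should decide.

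- **Option A, the body rule.** Replace synopsis item 11 with an exclusion of women who are pregnant or breastfeeding, and of WOCBP who lack a negative test in the 24 hours before first dose or do not accept the contraception set out in 4.2.1. In 6.1 and 6.3 item 3, add a urine or serum hCG for WOCBP after AF diagnosis and before randomization, timed to fall within that window. State in 4.2.1 that the pre-procedure test does not replace it.
- **Option B, the synopsis exclusion.** Enter in 4.2.2 an exclusion of pregnant women and of WOCBP as defined in 4.2.3, word item 11 to match, and delete the text admitting WOCBP. The contraception provisions for male participants stay.

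Either option is a single wording amendment. Option A also adds one hCG per WOCBP; option B narrows eligibility by what is probably a very small number. Neither alters the sample size or the analysis.

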4 INVESTIGATIONAL PLAN

4.1 Study Design and Duration

Planned study design: prospective, controlled, randomized pilot study

Screening procedures/study population: Patients will be eligible for screening if they develop atrial fibrillation in the postoperative period that:

1. Persists 12 hours or more.
2. Develop recurrent atrial fibrillation with two or more episodes of persistent AFib of at least 30 minutes duration during the same hospital stay.

Number of subjects per arm: 28

Randomization ratio/method: 1:1, determined in permuted block fashion

Duration of treatment: 30 days of oral anticoagulation therapy. This period will start with the first dose of anticoagulation (either apixaban or warfarin) given in the hospital, and continue until the patient's 30-day post-operative appointment.

Criteria for evaluation:

- Efficacy: systemic thromboembolism or stroke will be assessed retrospectively after the patient has completed the 30-day course of therapy.
 - Events relating to thromboembolism or stroke will be adjudicated using pre-determined definitions by independent committee members that remain blinded to the patient's treatment arm.
- Safety: major bleeding will be as defined by the Society on Thrombosis and Haemostasis, as follows:
 - 1. Fatal bleeding, and/or
 - 2. Symptomatic bleeding that occurs in a critical area or organ, such as intracranial, intraspinal, intraocular, retroperitoneal, pericardial, in a non-operated joint, or intramuscular with compartment syndrome, assessed in consultation with the surgeon, and/or
 - 3. Extrasurgical site bleeding causing a fall in hemoglobin level of 20 g/L (2g/dL) or more, or leading to transfusion of two or more units of whole blood or red cells within 24-48 hours of the bleeding and/or
 - 4. Surgical site bleeding that requires a second intervention – open, arthroscopic, endovascular- or a hemarthrosis of sufficient size as to interfere with rehabilitation by delaying mobilization or delayed wound healing, resulting in prolonged hospitalization or a deep wound infection, and/or
 - 5. Unexpected surgical site bleeding, prolonged and/or sufficiently large to cause hemodynamic instability, as assessed by the surgeon, with a fall in hemoglobin of at least 20 g/L (2g/dL) or transfusion of two or more units of whole blood or red cells within 24 hours of the bleeding.³

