In the hospital, bleeding will be assessed daily by monitoring hemoglobin and the need for transfusions. After discharge and until the patient's 30-day post-operative evaluation, we will monitor for readmissions related to bleeding, indicated by the need for transfusion of at least two units of blood products. Any patient phone calls that already occur as part of routine post-operative care will continue; however, there are no additional post-discharge phone calls to the patient related to this study.

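### The synopsis names ISTH as the bleeding definition, then defines in-hospital bleeding by a different rule; sections 4.1 and 6.3 do not match it, and nothing says which governs

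*Combined protocol and SAP*

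**What the plan says.** The Data Analysis Plan row of the synopsis sets the standard: "Safety events, including major bleeding will be as defined by the International Society on Thrombosis and Haemostasis". The sentence that follows says bleeding in hospital is assessed daily and is "defined by a drop in hemoglobin of > 2 gm/dL in the previous 24 hours, or transfusion of at least two units"; the units may be of any blood product. For the period after discharge it adds: "After discharge, we will monitor for readmissions related to bleeding, indicated by the need of transfusion of at least two units of blood products".

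The body of the protocol lists the ISTH major-bleeding criteria twice, in 4.1 and in 6.3. There are five:

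- fatal bleeding;
- critical-site bleeding ("Symptomatic bleeding that occurs in a critical area or organ");
- extrasurgical bleeding that meets one of two alternatives. The hemoglobin alternative reads "Extrasurgical site bleeding causing a fall in hemoglobin level of 20 g/L (2g/dL) or more". The transfusion alternative, as worded in 6.3, reads "leading to transfusion of two or more units of whole blood or red cells within 24-48 hours of the bleeding";
- surgical-site bleeding that needs a second intervention, or a hemarthrosis with stated consequences;
- unexpected surgical-site bleeding with hemodynamic instability plus a hemoglobin or transfusion criterion.

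Item 2 of 6.3 adds a residual category for any other notable bleed.

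After its list, 4.1 returns to the in-hospital sentence without any numeric rule: "In the hospital, bleeding will be assessed daily by monitoring hemoglobin and the need for transfusions". It keeps the post-discharge wording: "we will monitor for readmissions related to bleeding, indicated by the need for transfusion of at least two units of blood products".

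The Criteria for Evaluation row of the synopsis sends the reader to 6.4.2, item 2, for the bleeding definition. That item is post-operative length of stay.

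**The concern.** Major and minor bleeding to day 30 are named safety outcomes (2.1), and bleeding is part of the research hypothesis (1.3). Section 6.1 says outcomes other than compliance are taken from the electronic record after follow-up ends, so the written rule carries much of the weight in deciding what is counted. Blinded committee adjudication is specified for thromboembolism and stroke only (4.1, 6.4.1); no committee is named for bleeding.

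A person abstracting records from the synopsis clause and one working from 6.3 could therefore report different in-hospital bleeding counts for the same patients. The trial does not claim power to compare arms, so its descriptive counts are its main safety product. Section 9.1 offers the study as a reference for later trials, whose planners would take the counts to be ISTH counts.

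**Working it through.** The plan gives no figure to reproduce here: no bleeding rate is stated, and the question is one of definition. The check sets the two rules side by side and then runs constructed cases through both.

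**Where the rules differ**

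| Feature | Synopsis in-hospital clause | 4.1 and 6.3 (ISTH) |
|---|---|---|
| Bleed required | No | Yes |
| Hemoglobin fall | > 2 g/dL | ≥ 2 g/dL |
| Time limit on the fall | 24 h | None stated for the extrasurgical criterion |
| Units counted | Any blood product | Red cells or whole blood |
| Fatal, critical-site, re-intervention | Must still meet a threshold | No threshold |

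**Constructed in-hospital cases** (falls in g/dL; transfused units given on one day, so the result does not depend on whether the 24 h window also covers the transfusion part of the clause)

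| Case | Clause | 6.3 major |
|---|---|---|
| Extrasurgical bleed, fall 2.0, no transfusion | No: 2.0 > 2 is false | Yes: 2.0 ≥ 2 |
| Extrasurgical bleed, fall 1.2 on each of two days, no transfusion | No: 1.2 > 2 is false on each day | Yes: 1.2 + 1.2 = 2.4 ≥ 2 |
| Symptomatic intracranial bleed, fall 0.5, no transfusion | No | Yes: critical site |
| Surgical-site bleed with re-intervention, fall 1.5, 1 red-cell unit | No: 1.5 > 2 and 1 ≥ 2 are false | Yes: re-intervention |
| Two platelet units, no bleed | Yes: 2 ≥ 2 | No |
| Fall 2.5 in 24 h, no bleed | Yes: 2.5 > 2 | No |
| Extrasurgical bleed, fall 3 in 24 h | Yes | Yes |
| Extrasurgical bleed, 2 red-cell units | Yes | Yes |

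The second case holds even if the 24-48 hour phrase in the extrasurgical criterion is read as covering the hemoglobin fall, because 2.4 g/dL is reached within 48 h.

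**Non-major bleeds.** A notable bleed with a fall of 2 g/dL or less in 24 h and fewer than two units belongs in item 2 of 6.3. The clause says it is not bleeding at all.

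**Scale of one error.** With 28 patients planned per arm (4.1), one misclassified patient moves that arm's proportion by 1/28 = 3.6 percentage points. The cases show that the rules differ in both directions. They were chosen to test the boundaries and say nothing about how often such events would occur.

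**The case against.** The strongest reply is that the governing standard is clear enough. ISTH is named in the synopsis, in 2.1, in 4.1 and in 6.3, and its major-bleeding criteria are written out twice. Section 4.1 places the in-hospital sentence directly after one of those lists and omits the defining words, so the clause is probably loosely worded surveillance. As a reading of intent this stands. It does not remove the conflict: the synopsis says the event is defined this way, no section calls the clause a trigger or gives 6.3 precedence, and the pointer that should settle the matter leads elsewhere.

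A second reply is that the clause defines bleeding, not major bleeding, so a mismatch with the major criteria is not in itself an error. This matters for one item only. The omission of non-major bleeds arises only if the clause defines all bleeding. The missed major bleeds and the patients counted without a bleed arise on either reading.

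Third, 4.1 and 6.3 call for the surgeon's input on critical-site bleeds and on unstable surgical-site bleeds, so abstraction is not purely mechanical. That is true for those two criteria, but the other three carry no such step.

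A reader might infer that the post-discharge two-unit wording also redefines bleeding and must under-count it. The documents do not support that. The sentence speaks of monitoring. Section 6.1 schedules bleeding monitoring at the 30-day examination, and 7.1 and 7.1.1 require collection of serious events, including deaths and admissions, to 30 days after dosing stops. The direction of error would not be fixed either: two plasma units during a bleeding-related readmission would over-count major bleeds.

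A reader might also want to express the mismatch as a share of the ISTH criteria. Any such share depends on how criteria joined by an alternative are split and on whether the 24-hour window extends to transfusion, so none is given.

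**Conclusion.** The point holds as an inconsistency in the definition of a named safety outcome, and it should be fixed. It lies in one clause of the synopsis Data Analysis Plan and is made worse by a wrong cross-reference. If that clause is used to count events, it can miss ISTH major bleeds and non-major bleeds, and it can count patients who did not bleed. The post-discharge wording needs clarification only.

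The conclusion assumes that someone could apply the clause as written; the parallel sentence in 4.1 suggests this was not the intent. The number of patients affected cannot be estimated, because the documents give no bleeding rate. A reader might infer that the clause favors one arm. Nothing here shows that: it applies to both arms alike.

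**What to change.** - **Synopsis, Data Analysis Plan, in-hospital sentence:** delete the hemoglobin and transfusion thresholds as a definition, or restate them as a prompt for chart review. If they stay as a prompt, state the time window and the hemoglobin value from which the fall is measured.
- **Synopsis and 4.1, post-discharge sentence:** state that the two-unit wording is a surveillance prompt and not a rule for counting events.
- **Add:** *All bleeds found by any existing route, in hospital or after discharge and in both arms, are classified by the criteria in section 6.3.*
- **Synopsis, Criteria for Evaluation:** change the pointer from 6.4.2, item 2, to 6.3.
- **Leave unchanged:** the criteria in 6.3, and the separate outcome of units transfused (2.1; 6.4.2, item 1), which rightly covers all blood products.

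The cost is a wording change and somewhat more review of records that are already examined, with no new visits or patients. One limit remains: 2.1 lists minor bleeding separately from clinically relevant non-major bleeding, while 6.3 has a single non-major category. This change does not settle how those labels correspond.
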